### Extended Lane and Sandhu Scoring (eLSS) scale

Radiographic criteria		
Bone Formation		Distal radius
complete longitudinal defect		0
up to 25% of the longitudinal gap filled against the baseline		1
up to 50% of the longitudinal gap filled against the baseline		2
up to 75% of the longitudinal gap filled against the baseline		3
up to 100% of the longitudinal gap filled against the baseline		4
100% of the longitudinal gap filled against the baseline.		5
Bone remodeling		
no evidence of remodeling against the baseline		0
possible remodeling of intramedullary canal		1
full remodeling of the intramedullary canal and cortex		2
Bone Union		
complete transverse defect		0
up to 25% of the transverse gap filled against the baseline		1
up to 50% of the transverse gap filled against the baseline		2
up to 75% of the transverse gap filled against the baseline		3
up to 100% of the transverse gap filled against the baseline		4
100% transverse gap filled - complete absence of a fracture line.		5
Total LSS score per region		
	Min-max	0-12

4.5	Concomitant Treatments	23
4.5.1	Concomitant Medications	23
4.5.2	Concomitant Therapy.....	23
4.6	Sample Description	23
4.6.1	Disposition of Patients	23
4.6.2	Protocol Deviations	23
5	Overview of Assessments.....	24

List of Abbreviations

AE	Adverse Event
AESI	Adverse Event of Special Interest
CI	Confidence Interval
CRF	Case Report Form
CSR	Clinical Study Report
CT	Computed Tomography
D	Day
DECT	Dual Energy Computed Tomography
DRF	Distal Radius Fractures
eLSS	extended Lane and Sandhu Scoring
ETV	Early Termination Visit
FU	Follow-Up
HD	Hospital Discharge
HIV	Human Immunodeficiency Virus
ICH	International Council for Harmonization
IMP	Investigational Medicinal Product
INN	International Nonproprietary Names
IS	Implant Surgery
M	Month
MedDRA	Medical Dictionary for Regulatory Activities
MMWS	Modified Mayo Wrist Score
NRS	Numeric Rating Scale
PoC	Proof-of-Concept
PT	Preferred Term
PRWE	Patient-Rated Wrist Evaluation
rAESI	Reportable Adverse Event of Special Interest
SAE	Serious Adverse Event
SAF	Safety Set
SAP	Statistical Analysis Plan
SOC	System Organ Class
TEAE	Treatment Emergent Adverse Event
V	Visit
W	Week

1 Introduction

The purpose of the present Statistical Analysis Plan (SAP) is to precisely define the statistical analysis of the data of the study NVDX3-CLN01 (EudraCT number 2022-002304-21/CT number: 2023-508321-27-00). This SAP will cover the analysis of the primary and secondary endpoints.

The SAP is based on the study protocol, version 6.0 (dated 25 June 2023) and the annotated CRF, version 5.0 (dated 21 March 2024). The SAP is prepared in compliance with ICH E9.

Any changes to the planned analyses occurring after finalization of the SAP will be described and justified in the Clinical Study Report (CSR).

1.1 Study Design

This study is a prospective, single arm, monocentric first-in-human Proof of Concept study in adult patients, suffering from a distal radius fracture, treated during the surgical intervention with NVDX3, an osteogenic implant from human allogeneic origin.

A patient is considered evaluable once he/she underwent the implant surgery with NVDX3.

As per standard of care, patients with DRF are followed up to 3 months post-intervention. In the context of this trial, patient safety and IMP efficacy will be followed up to 12 months post-implant surgery.

At the end of this study, the included patients will be invited to participate in a long-term safety follow-up study for an additional period of 10 years.

The study consists of the following phases:

- Screening (V1)
- Acute Safety FU
 - o Implant Surgery - IS (V2)
 - o Hospital Discharge - HD (V3)
 - o Visit 4 (W2)
 - o Visit 5 (W6)
- Mid-term¹ Safety FU
 - o Visit 6 (M3)
 - o Visit 7 (M6)
 - o Visit 8 (M12)

1.2 Objectives of the Study

1.2.1 Primary Objective

The primary objective of this PoC study is to assess the safety of the NVDX3 implant.

1.2.2 Secondary Objective

The secondary objectives of this study are the following:

- To assess the acute and mid-term¹ safety of the NVDX3 implant.
- To assess the efficacy of the NVDX3 implant radiologically and clinically

1.2.3 Exploratory Objective

¹ "Mid-term follow-up" will replace "long-term follow-up" in the core study NVDX3-CLN01 to differentiate this time period from that of the long-term follow-up study, NVDX3-CLNOX, as detailed in Section 3.6.

1.3 Study Endpoints

1.3.1 Primary Endpoint

The primary endpoint is the evaluation of all SAEs and NVDX3 related AEs between screening (V1) and 12 months post-IS (V8).

1.3.2 Secondary Endpoints

1.3.2.1 Safety

- Description of all acute SAEs and NVDX3 related AEs between screening (V1) and 6 weeks post-IS (V5).
- Description of all Serious TEAEs and NVDX3 related TEAEs beyond 6 weeks (V5 excluded) until 12 months post-IS.
- Description of Treatment Emergent AEs (TEAEs) for the periods:
 - Between IS² and week 6 (V5 included)
 - Between week 6 (V5 excluded) till month 12 (V8 included)
 - Full study duration
- Description of related and unexpected AEs between inclusion* and study completion (TEAEs).
- Description of related and unexpected Serious AEs between inclusion* and study completion (serious TEAEs).
- Description of AEs of Special Interest between inclusion* and study completion (TEAESIs).
- Description of lab data and vital signs obtained between inclusion* and study completion.

*Inclusion refers to Implant Surgery, i.e. when the NVDX3 was implanted.

1.3.2.2 Efficacy

Radiological assessments on Computed Tomography data (CT) using the extended Lane and Sandhu Scoring tool (eLSS)

The following assessments will be performed at 3 and 12 months post-IS.

- Evaluation of bone formation status
- Evaluation of bone union status
- Evaluation of bone remodeling status
- Evaluation of Total extended Lane and Sandhu Score

Assessments will be compared to HD.

Radiological assessments on X-ray Using the eLSS tool

The following assessments will be performed at 2 and 6 weeks and at 3, 6 and 12 months post-IS according to standard of care.

- Evaluation of bone formation status
- Evaluation of bone union status
- Evaluation of bone remodeling status
- Evaluation of Total extended Lane and Sandhu Score

Assessments will be compared to HD³.

² The assessment period for the acute events has been changed compared to the protocol, as detailed in Section 3.6.

³ The baseline timepoint has been changed compared to the protocol, as detailed in Section 3.6.

Clinical assessments

The following assessments will be performed at HD, at 2 and 6 weeks and at 3, 6, and 12 months post-IS:

- Grip strength measure with a hydraulic hand dynamometer
- Modified Mayo Wrist Score (MMWS): A physician-based scoring evaluating the patients' pain, active flexion/extension arc, grip strength and ability to return to regular employment or activities.
- PRWE Questionnaire: A patient reported scoring evaluating the patients' wrist pain and disability.

The post-HD assessments will be compared to HD.

Numeric Rating Scale (NRS) for pain, a patient reported scoring evaluating the patients' pain, will be performed at screening, at HD and 2 and 6 weeks, 3, 6, and 12 months post-IS.

The post-screening assessments will be compared to screening.

1.3.3 Exploratory Endpoints

- [REDACTED]
- [REDACTED]
- [REDACTED]
- [REDACTED]

1.4 Sample Size Justification

No formal sample size calculation has been performed for this study since no formal hypothesis will have to be tested. However, as this is an early phase Proof of Concept study, the number of patients was limited to 10 individuals.

2 Data Considered for the Analysis

2.1 Patient Characteristics

At screening the following information is collected:

2.1.1 Demographic Data

- [REDACTED]
- [REDACTED]
- [REDACTED]
- [REDACTED]

2.1.2 Contraception Data

- [REDACTED]
- [REDACTED]

2.1.3 Smoking History

- [REDACTED]
- [REDACTED]
- [REDACTED]

- [REDACTED]
- [REDACTED]

2.1.4 Employment Data

- [REDACTED]
- [REDACTED]

2.1.5 Index Fracture Classification

[REDACTED]

2.1.6 Medical History

- [REDACTED]
- [REDACTED]
- [REDACTED]

2.2 *Study Treatment Data*

2.2.1 Implant Surgery

If 'Yes', [REDACTED]

2.2.2 Drug Accountability

1. **What is the primary purpose of the study?**

2.3 *Efficacy*

2.3.1 Central Review CT using eLSS

A high-contrast, black and white abstract image. The composition is dominated by a large, dark, irregular shape on a white background. This dark shape is formed by several thick, horizontal black bars of varying lengths. On the left side, there are vertical black bars of different heights, creating a stepped or layered effect. The right side of the image is mostly white, with a few small, isolated black shapes. The overall effect is minimalist and geometric, resembling a stylized landscape or a abstract architectural drawing.

2.3.2 Central Review X-Ray

2.3.2.1 Efficacy assessment using eLSS:

Category	Count
1	1
2	1
3	1
4	1
5	1
6	1
7	1
8	1
9	1
10	1

2.3.2.2 Peri-operative measurements

⁴ The baseline timepoint has been changed compared to the protocol, as detailed in Section 3.6.

2.3.3 Clinical Assessments

2.3.3.1 Grip Strength Test

[figure not shown]
2.3.3.2 Physician reported Modified Mayo Wrist Score

2.3.3.3 Patient reported Numerical Rating Scale for Pain

2.3.3.4 Patient-Rated Wrist Evaluation

2.4 Safety

2.4.1 Adverse Events

Information on adverse events will be collected throughout the study.

■. If 'Yes':

Adverse events are coded

Any medical condition that is present at the time of the patient's screening will be considered as Medical History and not reported as an AE. [REDACTED]

2.4.1.1 Acute Adverse Events

An acute adverse event is defined as an event that starts on or after the Implant Surgery (V2) till 6 weeks post-IS (V5 included).

2.4.1.2 Mid-term Adverse Events

A mid-term adverse event is defined as an event that starts after 6 weeks post-IS (V5 excluded) till study completion (completion V8 or early termination whichever comes first).

2.4.1.3 Treatment-emergent adverse events (TEAEs)

A Treatment-emergent adverse event (TEAE) is defined as an event that emerges after the NVDX3 was implanted, having been absent pre-implant surgery, or worsens relative to the preimplant state.

In case an event starts at the date of the surgery it will be decided at the DRM if the event can be considered as prior or treatment emergent based on input from the sites.

In case of a partial or missing date for the start of an adverse event it will be assumed that the event was treatment-emergent unless it can be determined from the partial start or stop date that the event definitely started before the NVDX3 was implanted.

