## 6. STUDY SCHEDULE

### 6.1. Schedule of Activities Table

	Screening	Acute safety FU					Long-term safety FU			Early Termination ETV
		V1	V2 	V3	V4	V5	V6	V7	V8	
					W2	W6	M3	M6	M12	
			Implant Surgery IS (Max 7 days after DRF diagnosis)	Hospital Discharge HD	IS+13d ± 2d	IS+42d ± 7d	IS+90d ± 15d	IS+180d ± 30d	IS+360d ± 30d	
Informed consent		x								x 
Eligibility criteria		x								x 
Demography		x								
Medical and concomitant medication history		x								
Index fracture evaluation/classification		x								
Physical examination		x	x	x	x	x	x	x	x	x
Weight/Height (BMI) 		x	x	x	x	x	x	x	x	x
Triplectate 12-Lead ECG			x							x
Vital signs		x	x	x	x	x	x	x	x	x
Inspection of the skin of the affected arm 		x	x	x	x	x	x	x	x	x
Standard safety laboratory 		x		x	x	x	(x)	(x)	(x)	
Serology (HIV, HBV & HBC)		x								
Pregnancy test 		x								x
Implant Surgery (IS)			x 							
Peri-operative IS related information			x							
Grip strength test				x	x	x	x	x	x	x
NRS-pain		x		x	x	x	x	x	x	x
PRWE				x	x	x	x	x	x	x
MMWS				x	x	x	x	x	x	x
Radiological efficacy 	AP/LAT X-ray	x*	x 7*	x*	x*	x*	x*	x*	x	x
	DECT-scan	x* (Normal CT)		x			x		x	
AE/SAE collection			x	x	x	x	x	x	x	x
Concomitant medication			x	x	x	x	x	x	x	x
Concomitant therapy				x	x	x	x	x	x	x

1 In-clinic stay: The patient may be hospitalized before the surgery following to hospital standard of care. The required pre-operative assessments can be done up to 3 days before the surgery.

2 Skin inspection to evaluate potential surgical site infections.

3 At screening, Discharge, V4 and V5: safety laboratory analyses are mandatory. At V6, V7 and V8: Upon occurrence or any suspicion of safety related issues.

4 In women of childbearing potential only: a serum pregnancy test will be performed at Screening and at V8

5 Follow the instructions ad per "NVDX3 handling Manual".

6 To guarantee image quality, all X-rays and CT-scan acquisitions will need to strictly follow the imaging instructions as described per "Imaging Acquisition Manual".

7 AP/LAT X-rays: both after insertion of fixation device, and after insertion of the NVDX3 implant (at the end of the surgery)

8 Height at screening only

9 Informed consent proposing participation to the long-term safety follow-up study (NVDX3-CLNOX)

\* Standard of care image acquisitions for the diagnosis and follow-up of DRF

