#### **8.2.4. Adverse Event reporting**

When an AE occurs, the Principal Investigator, or defined delegate(s), will review all documentation (e.g., hospital progress notes, laboratory reports, and diagnostics reports) related to the event and record all relevant AE information in the eCRF.

**All AEs including local and systemic reactions not meeting the criteria for SAEs will be captured on the case report form (eCRF) within 5 working days of event awareness.**

Information to be collected includes event description, time of onset, investigator's assessment of severity, relationship to surgical procedures and trial product (assessed only by those with the training and authority to make a diagnosis), and time of resolution/stabilization of the event.

AEs occurring while on trial must be documented appropriately regardless of relationship.

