2.4.1.4 Related Adverse Events

For each type of causality (NVDX3, grafting surgery, other study procedure) an adverse event is considered related if it is assessed as possibly, probably or definitely related or if the assessment is missing.

An adverse event will be considered NVDX3-related only in case the causality is NVDX3. It is not NVDX3-related if the cause is the grafting surgery or other study procedure.

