4.5 Concomitant Treatments

4.5.1 Concomitant Medications

Medication that ends on the date of surgery will be considered as concomitant. Prior medication will only be these medications clearly stopping before the date of surgery.

A table will be provided showing frequency distributions of patients taking concomitant medication by anatomical class and therapeutic class for the SAF.

A listing will be provided for all medications.

A separate listing will be provided for pain medications.

In both listings it will be indicated whether the medication started before or after the start time of surgery.

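### SAP 2.4.1.4 lacks the word *alone*, so an AE attributed to both NVDX3 and the surgery may not count as NVDX3-related; SAP 2.4.1.3 also has no fallback for surgery-date AEs of unclear sequence (minor)

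*SAP*

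**What the plan says.** **Relatedness (SAP 2.4.1.4).** The section names three types of causality: NVDX3, grafting surgery and other study procedure. For each type, "an adverse event is considered related if it is assessed as possibly, probably or definitely related or if the assessment is missing". It then makes NVDX3 causality the condition for calling an event NVDX3-related, and closes: "It is not NVDX3-related if the cause is the grafting surgery or other study procedure".

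Two other places depend on this flag. SAP 1.3.1 defines the primary endpoint as all SAEs plus NVDX3-related AEs, from screening to month 12. SAP 2.4.1.5 defines a reportable AESI (rAESI) by the investigator's rating of relation to NVDX3 and does not cancel it when there is a second attribution.

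**Surgery-date events (SAP 2.4.1.3).** A TEAE is "an event that emerges after the NVDX3 was implanted, having been absent pre-implant surgery, or worsens relative to the preimplant state". Onset on the day of surgery has a separate rule: if "an event starts at the date of the surgery it will be decided at the DRM if the event can be considered as prior" rather than treatment-emergent. That decision rests on site input. I take the DRM to be the data review meeting; the abbreviation list does not define it. For a partial or missing start date, by contrast, "it will be assumed that the event was treatment-emergent unless it can be determined from the partial start or stop date" that onset was definitely before implantation.

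**Timing data.** Protocol 8.2.4 says: "Information to be collected includes event description, time of onset". Footnote 7 of the schedule in Protocol 6.1 calls for X-rays after the fixation device is placed and again after NVDX3 is inserted, at the end of surgery.

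**The concern.** NVDX3 is given once, during the operation. An early event may therefore be hard to attribute to the implant rather than to the surgery, and an investigator may well rate both as possible causes. The first sentence of 2.4.1.4 allows this. The last sentence, applied as written, then removes the event from the NVDX3-related group because the surgery is also a cause. In a first-in-human study with safety as the primary objective, the flag that feeds the primary endpoint should not depend on how a programmer reads one sentence.

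The surgery-date rule raises a smaller version of the same worry. The surgery date includes operating time before implantation, so a complete onset date does not by itself show which came first. Where the sequence stays unclear, classification is a case-by-case decision by people who know the event, in a single-arm study. A missing date gets a conservative default; a known date on the day of exposure does not.

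**Working it through.** The plan states no figure on this point, so there is none to reproduce. The check is a logic count and a trace through the outputs.

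**Inputs.** SAP 2.4.1.4: three causality types, a missing rating counting as related. SAP 4.4.1: 12 overview rows, 3 SOC/PT tables, and 4 listings, 3 of them TEAE-based. SAP 1.4: 10 patients.

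**Step 1: rating patterns.** Each causality type can be related, unrelated or missing, which gives 3 × 3 × 3 = 27 patterns.

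- First sentence of 2.4.1.4: NVDX3 related or missing, the other two anything: 2 × 3 × 3 = 18 patterns are NVDX3-related.
- Last sentence taken literally, with missing counted as related throughout: both other types must be unrelated, so 2 × 1 × 1 = 2 remain and 18 − 2 = 16 are reversed. The 16 include the pattern with all three ratings missing, which defeats the conservative missing-data rule.
- Literal, but with a missing surgery or procedure rating not treated as a cause: 2 × 2 × 2 = 8 remain and 10 are reversed.
- With *alone* added: all 18 remain.

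These are logical possibilities, not expected frequencies.

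**Step 2: one event traced through SAP 4.4.1.** Take a treatment-emergent hypersensitivity AE that is non-serious, non-severe and expected, and is rated possibly related to both NVDX3 and the grafting surgery, but unrelated to any other procedure.

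| Output | Per-type rule, or with *alone* | Literal last sentence |
|---|---|---|
| Row: any TEAE | in | in |
| Row: NVDX3-related TEAE | in | **out** |
| Row: related to grafting surgery | in | in |
| Row: treatment-emergent AESI | in | in |
| Row: treatment-emergent rAESI | in | in |
| Overview rows in total | 5 | 4 |
| SOC/PT tables | 3 | 2 |
| Listings | 2 | 2 |
| Primary endpoint | in | **out** |

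On the literal reading, one overview counts the event as reportable because it is related to NVDX3 and also leaves it out of the NVDX3-related row.

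**Step 3: a surgery-date AE ruled prior.** The 2.4.1.3 default is triggered by a partial or missing start date. A complete date equal to the surgery date does not meet that trigger, so no default applies.

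- Smallest effect (non-serious, non-severe, expected, unrelated, not an AESI): the event leaves 1 row, 2 tables (all TEAEs; TEAEs by maximal severity) and 1 listing.
- A serious, non-severe, expected AE related to the grafting surgery only: it leaves 3 rows (any, serious, surgery-related), 2 tables and 2 listings. If it is unexpected, 3 + 2 = 5 rows.

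In each case it moves to the listing of non-treatment-emergent AEs. The primary endpoint starts at V1, so its definition does not depend on this classification.

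**Step 4: size.** 1/10 = 10 percentage points if the reclassified event is the patient's only one in that row, and 0 if the patient has another event there.

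**The case against.** **On relatedness.** The closing sentence can be read as referring to a sole cause. The sentences before it judge each type separately and make NVDX3 causality the test, and SAP 4.4.1 gives the three types separate rows. Its likely purpose is useful: Protocol 8.1.7 groups the implant, the implant procedure and other procedures under one relationship heading, and the SAP makes clear that attribution to surgery does not by itself implicate the product. This stands, so the sentence is ambiguous rather than certainly wrong. A reader might infer that the SAP definitely excludes every dual-attribution event; the text does not establish that.

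**On surgery-date events.** The SAP already has a criterion, a forum and an evidence source, and onset time is collected. The surgery fields and some AE fields are redacted, so a before-or-after-implantation item cannot be ruled out. The SAP's reference to the start time of surgery, in 4.5.1, concerns medication and says nothing about how AEs are timed. A data-review decision is a legitimate choice in a small descriptive study. All of this stands and confines the gap to cases that site input cannot settle, which may be few.

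**Stronger inferences.** A reader might infer that a prior ruling hides events or takes them out of the primary endpoint. The documents do not support this: the endpoint runs from screening, and the event remains listed. A reader might also infer that such a ruling could empty all 12 overview rows for an event. That would need an event the investigator rates as related to NVDX3 and that is also placed before implantation on the same site's input, which is not plausible.

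**Conclusion.** Both points hold as wording defects, and the severity is minor.

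The relatedness sentence is the main one. Followed exactly, it can give a wrong result: a dual-attribution AE leaves the NVDX3-related outputs and, if non-serious, the primary endpoint, while possibly remaining an rAESI. The missing surgery-date default is secondary; it concerns only where an event is presented among the AE outputs.

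No event disappears from the listings under either point. The documents do not say how many events would be affected, so reclassification of one patient is an assumption made for scale, and the 10-point shift carries the condition in Step 4. No hypothesis is tested, so sample size, power and type I error are untouched.

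**What to change.** **SAP 2.4.1.4.** Replace the last two sentences with: *An AE is NVDX3-related if its NVDX3 causality is possible, probable, definite or missing, whatever its other attributions; attribution to the grafting surgery or another procedure alone does not make it NVDX3-related.*

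**SAP 2.4.1.3.** Replace the surgery-date rule with: *An AE starting on the surgery date is treatment-emergent unless the record shows that it started before NVDX3 was implanted and did not worsen afterwards; if the sequence is unclear, it is treatment-emergent.* An event can still be classed as prior at the DRM when the record shows it.

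**Cost.** Two short edits before database lock, with no new data and no new table. If the SAP is already final, SAP section 1 requires the change to be described and justified in the CSR. The downside is possibly slightly higher counts of treatment-emergent and NVDX3-related events.
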